***C. difficile* near-patient testing versus centralized laboratory testing: a cluster randomized study**

Principle Investigator: [name]

Other Investigators: [name], [name], . [name], [name], [name], [name], [name], [name], [name], [name], [name]

Institutional Affiliation: University of Calgary, Alberta Health Services, Calgary Laboratory Services

Funding: Canadian Institute of Health Research

Background and Significance:

Antimicrobial resistance (AMR) has been designated as a major priority by the World Health Organization (WHO), Centers for Disease Control and Prevention (CDC) and the Public Health Agency of Canada (PHAC). PHAC has identified *Clostridium difficile* infection (CDI) as a Tier 1 AMR priority pathogen. CDI occurs directly as a consequence of antibiotic use and falls under the clinical syndrome of antibiotic-associated diarrhea (AAD). It is the most common cause of infectious diarrhea among hospitalized patients in developed countries like Canada (Skidmore, 1993). The economic cost of CDI in the United States is estimated at USD 5.4 billion, close to 87% of which occurs in healthcare settings (Desai et al., 2016). CDI epidemics in the last two decades have resulted in significant morbidity and mortality especially in the elderly (Miller et al., 2010). In particular, the emergence and dissemination of a hypervirulent strain (North American Pulsotype (NAP) 1) has resulted in hospital outbreaks and increased mortality in the elderly (Loo et al., 2005). NAP 1 carries genetic resistance to commonly used antibiotics for pneumonia and may have spread due to the overuse of certain classes of antibiotics that select for this strain (McDonald et al., 2005; Pillai et al., 2010). As CDI is strongly associated with previous antibiotic use, antimicrobial stewardship is believed to have a role in preventing and terminating CDI outbreaks.

Diagnostic methodology has evolved rapidly in the last decade. The European Society of Clinical Microbiology and Infectious Diseases recently provided recommendations on diagnostic testing for CDI but questions remain (Crobach et al., 2009). Early testing approaches relied on detection of the toxin using a neutralization assay (TNA). In this approach, stool supernatants are evaluated for the presence of toxin by plaque formation on lawns of mammalian cells. The presence of CDI toxin was confirmed by the ability of anti-toxin to neutralize CDI toxin effects. The method took 3 to 4 days to complete and required a cell culture facility no longer commonplace in diagnostic laboratories. TNA was soon replaced by enzyme immune assays (EIA) that do not require cell culture and could be performed in 2-3 hours. However, as the epidemic of NAP 1 swept through North America and Europe it became very clear that the EIA lacked sensitivity and missed cases, prompting physicians to repeat testing. EIAs were advantageous in terms of ease of use, turnaround time, and cost. Toxin antigen detection could also be performed using rapid diagnostic tests (RDT) such as lateral flow assays. However, EIA and RDT both suffered a lack of sensitivity and, in some cases, specificity (Novak-Weekley et al., 2010). With the NAP 1 epidemic, molecular assays were emphasized with their increased sensitivity. These nucleic acid amplification tests (NAATs) are able to detect very low levels of bacteria and have emerged as the predominant test in the last five years (Gould et al., 2013). However, NAATs are costly and so clinical microbiologists have developed a two-step algorithm in which an EIA or RDT is first used to screen stools for the presence of glutamate dehydrogenase (GDH) antigen derived from *C. difficile*. The GDH antigen test is very sensitive (> 95%) and negatives could be reported right away, only requiring GDH-positive toxin negative specimens by EIA or RDT to be confirmed by NAAT. At CLS, the two-step algorithm is performed for a population of close to 1.5 million people at an offsite Diagnostic and Scientific Centre (DSC). The use of a testing centre, however, undermines to some extent the advantages of the

rapid testing methodologies developed in recent years, because of increased transportation and processing time.

A key issue in many settings, including ours, is that testing falls into a separate budget from the treatment of patients with CDI infections. This has the potential to distort the decision of whether to run a test and, if so, what sort of test. The distortions are of two types. First, the hospital may decide to order more tests than is optimal, since the tests are perceived as "free" from the perspective of decision-makers. At the same time, the diagnostic facility may choose low-cost, slow diagnostics, because the costs associated with delays in test results are borne by the hospital. This is a classic case of silos in health care costs inefficiently distorting policy decisions, with potentially negative results for both patient health and costs.

Many institutions follow the clinical practice guidelines provided by the Infectious Diseases Society of America for the management of *C. difficile* (Cohen et al., 2010). As part of routine Infection Prevention and Control (IPC) management, patients with acute diarrhea of unknown cause are pre-emptively placed in private rooms with additional contact precautions, which mandate the use of gowns and gloves for healthcare workers. This is also known as patient isolation. Investigation for gastrointestinal pathogens is typically initiated and the duration of patient isolation depends largely on the result of microbiological testing. When severe or complicated CDI is suspected, patients are initiated on empiric treatment as soon as the diagnosis is suspected. Generally, oral metronidazole is used for mild-to-moderate CDI and oral vancomycin for severe CDI. Among hospitalized patients with acute diarrhea, initiation of pre-emptive management for CDI is common. With requested CDI screening, 85% are negative on GDG screen and 89% are negative post PCR confirmation.

The intervention of interest is implementing a new RDT to Near Patient Testing (NPT); screening for CDI to be performed at the hospital rapid response laboratory (RRL) instead of the DSC. Techlab Inc. offers a lateral flow assay (C. DIFF QUIK CHEK COMPLETE® test) that detects both GDH and Toxin simultaneously and further simplifies the testing algorithm. As prescribed in the two-step algorithm, GDH and Toxin negatives will be reported out immediately as negative for CDI, while positive or discrepant results will be confirmed at the DSC using NAAT. The vast majority of requests for CDI testing are negative thus allowing a majority of results to be reported immediately to patient wards without NAAT confirmation at the DSC.

Study Objectives:

Calgary presents a unique opportunity to examine the effect of decentralizing CDI testing to Near Patient Testing. While it is not possible to perfectly duplicate the testing technology (described earlier) at NPT and the central laboratory, it is possible to provide equivalent testing. In a pilot study, we tested 20 stool samples by our current CLS centralized testing algorithm and anticipated NPT algorithm. Both algorithms rely on a two-step approach, namely GDH screen and molecular confirmation for toxin although the platforms are different. We had 100% concordance in the final result (presence of toxin) between the two algorithms. Further confirmation of this assumption (equivalence in performance) will be completed with a larger sample size prior to finalization of the NPT algorithm.

We will conduct a two-period, two-intervention, cluster randomized crossover (CRXO) design study at Foothills Hospital. Each cluster (ward) will receive each of the two interventions in a separate 6-month period of time leading to two “cluster-periods” with associated “wash-in” and “wash-out” periods attached. The interventions are RDT using NPT for CDI, and testing for CDI using centralized testing at the DSC.

This study is a cross-sectional CRXO in that, each cluster-period consists of different individuals (patients). The order in which the interventions are delivered to each cluster (ward) is randomized to control for potential period effects. Within Foothills Hospital there are 40 wards which will be observed over a 12-month period. Each ward is randomly assigned to administer one of the two interventions for the first 6-month period (Period 1). In the second 6-month period (Period 2), the ward will administer the other intervention. Within each ward (cluster) there are two cluster-periods. Study outcomes during Period 1 and Period 2 intervention will be compared in both arms (NPT and centralized laboratory testing).

NPT testing can deliver results within several hours, while typically off-site testing takes one to two days. If NPT and the off-site testing deliver identical test results as our pilot data suggest, we can follow the clinical outcomes for each arm without the confounder of differences in test performance. As a contingency, if variation in test performance characteristics is found, analysis of patient outcomes will take this into consideration.

For patients without CDI, the antibiotics, and in many cases, the isolation, are unnecessary. NPT testing has the potential to avoid this unnecessary use of antibiotics and to avoid costly isolation procedures for the day+ that standard testing requires. It also enables a better-directed diagnostic process for the cause of diarrhea. For patients who are positive for CDI, the earlier test result will influence downstream events such as initiation of antibiotic therapy, resolution of disease, hospitalization days, and other clinical outcomes.

We hypothesize that NPT for CDI will result in reduced patient isolation days in the hospital, decreased morbidity and mortality, reduced unnecessary antibiotic use and overall reduced costs to the health care system, including both hospital and laboratory.

Previous data has indicated that the mean number of patients a ward is 39/month ($SD=43$) for a total of 1578 patients in a 6-month period and the mean number of negative patients is 33/month ($SD=34$) for a total of 1300 negative pts in a 6-month period. The inclusion criteria will be diarrhea in adult patients admitted to four acute care hospitals in the Calgary region being tested for CDI. Outpatients and patients in the emergency room will be excluded.

Our primary endpoint is to examine the differential effect of NPT on the duration of contact precautions (i.e. patient isolation days). Secondary outcomes will compare turn-around times from specimen submission to result, days of hospitalization, the number of days of antibiotic therapy, the incidence of CDI, severe CDI, and in-hospital mortality. A comprehensive economic evaluation will be performed to determine the cost of testing, patient isolation, and hospitalization for all patients in the control and treatment arms.

Methods:

Contact precautions (i.e. patient isolation) due to CDI will be defined as an order by healthcare workers for contact precautions within the 7-day infection window of a CDI diagnosis. The length of time on contact precautions will be defined as the calendar date contact precautions are completed or patient discharge date minus the calendar date contact precautions are ordered. Data on contact precautions will be extracted from the clinical patient management system in Calgary, known as Sunrise Clinical Manager (SCM). It is used extensively in all Calgary acute care facilities and emergency departments. These data include patient identifiers (e.g. patient health number, names, date of birth), start and stop dates of isolation, facility, and patient care unit where isolation order was placed, and reason for isolation (e.g. CDI, diarrhea). These data will be linked to the specimen results tested for CDI by the patient's Personal Health Number (PHN). Turn-around times from specimen submission to result will be provided by Calgary Laboratory Services. Days of hospitalization will be defined as the difference between the admission and discharge date. The specimen results will be linked to the Discharge Abstract Database using the patient's PHN to determine during which acute care encounter the specimen was collected and the admission/discharge dates of that encounter. Antibiotic therapy will be defined as the administration of antibiotics initiated on the day of and up to 48 hours after specimen collection for CDI testing. Total days of antibiotic therapy during the acute care encounter will be defined as the calendar date antibiotic therapy is completed minus the calendar date antibiotic therapy is ordered. The data will be extracted from SCM.

We will also account for the severity of CDI. The epidemiological definition for severe CDI is that primarily proposed by Cohen *et al*. This definition has been used by infectious disease specialists in Alberta to guide the management and treatment of patients with CDI. Patients with severe CDI will have leukocytosis with a white blood cell (WBC) count $>15,000$ cells/ μ L OR an elevated serum creatinine (i.e. 200 μ mol/L or greater). The inpatient laboratory results that will be considered to meet the definition for severe CDI will be those collected within a 7-day infection window around the date the laboratory tested positive for *C. difficile*. The presence of either measure meeting the criteria within the defined infection window will qualify as meeting the definition of severe CDI. If either criterion is measured more than once during the infection window, the highest value will be used to represent the severity of CDI. The laboratory values will be provided by Calgary Laboratory Services and linked to the positive *C. difficile* test results. In-hospital, all-cause mortality will be defined as death occurring during the acute care encounter where specimens were collected for *C. difficile* testing.

We predict that, given the large number of patients and randomized study design, matching of patients by age, gender, and co-morbidities is not required. Potential hurdles in the study model are logistical challenges associated with building a testing and reporting system for a hospital on a 24hrs/7 days per week basis. The strength of the proposal lies in the scale and nature of the study which seeks to establish the medical and economic benefit of NPT versus centralized testing. The results could dramatically influence public health policy in this country and seek to bridge traditional silos, namely the laboratory and hospital budgets. Data on costs will be furnished by our partners at Calgary Laboratory Services and Alberta Health Services (Infection Prevention and Control).

Data Analysis:

In order to make the data generalizable to other settings, an appropriate econometric methodology to assess the impact of the impact of the NPT testing through multivariate regression is required. For example, consider the following potential model:

$$y_i = \beta_0 + \beta_1 POCT_i + \beta_2 Z_i + \beta_3 H_i + \beta_4 T_i + u_i$$

where y_i is the outcome variable of interest (such as the hours that a patient spends in isolation or the days of hospitalization); $POCT_i$ is a dummy variable indicating whether the patient had a NPT test; Z_i is a vector of individual-specific variables, including age, gender, CDI status and severity, and the like; H_i is a set of dummies indicating ward; T_i is a set of dummies indicating season or month; and u_i is an individual-specific error term. This approach allows us to identify the effect of NPT testing independent of patient, ward and season. In addition, the NPTT dummy can be interacted with other variables to see whether the impact of NPT testing is higher for certain types of patients

Beyond evaluating the relative merits of NPT versus centralized testing, studies will also look at the microbiology of CDI in this study. Specifically, we will conduct several laboratory methods to examine antibiotic resistance and genetic variation in CDI. For example, whole genome sequencing of cultured CDI isolates may inform us about the transmission of specific strains in our setting. Indeed, certain strains and states of gut dysbiosis may result in increased morbidity and mortality (Shahinas et al., 2012). We will look at the microbiome of patients in this study to determine if dysbiosis contributes to adverse clinical outcomes. We will also correlate the strain types with the results of testing to determine if genetic variation affects test performance. Cultured toxin-producing CDI isolates will serve as a gold standard to evaluate test performance.

Originality of the proposal:

It is our view that in the clinical laboratory arena NPT for CDI (described earlier) as a technology has already matured to a stage that translation of this technology into the clinical domain is now needed. As described previously, several formats including lateral flow are currently available through major diagnostic companies. The Infectious Diseases Society of America (IDSA) has recently recommended that rapid diagnostic testing can enhance antimicrobial stewardship by promoting appropriate antibiotic use for respiratory infections (Barlam et al., 2016). However, the recommendation is listed as “weak” with “low-quality evidence”.

This proposal directly aims to improve the evidence base for rapid diagnostic testing in this case for CDI. We will harness innovative new diagnostic tools in collaboration with industry partners to perform a cluster randomized clinical trial. We aim to demonstrate the clinical and economic impact of NPT for CDI, a major cause of morbidity and mortality in our hospitals. Previous

attempts to assess the impact of NPT for CDI have focused on intensive care unit and have been relatively small in sample size (Goldenberg et al., 2014). The innovation lies in the application of a cluster randomized trial model to NPT bridging the clinical laboratory and infection control domains in the hospital to assess the clinical and economic impact. We will leverage the existing infrastructure of one of the largest centralized laboratories in Canada namely Calgary Laboratory Services (Alberta Health Services) which provides testing to a population of 1.5 million people in Southern Alberta. The experimental arm will enable the use of NPT testing in the hospital. The total number of enrolled patients ($n \approx 3000$) will be one of the largest prospective analyses of NPT according to our reading of the literature. The large number of patients will permit a rigorous statistical evaluation of the significance of NPT technology for a key AMR organism. We believe this model can be expanded to other PHAC high priority Tier 1 antibiotic resistant organisms where NPT technology can be evaluated in a second phase.

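### Patients enter the analysis only if ward staff order a CDI test after allocation, so an arm difference in who is tested could bias the isolation-day comparison, and the plan has no check for it

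*Combined protocol and SAP*

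**What the plan says.** All references are to the combined protocol and SAP.

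- **Allocation (Study Objectives).** "Each ward is randomly assigned to administer one of the two interventions for the first 6-month period", and the other intervention follows in the second period. "Within Foothills Hospital there are 40 wards which will be observed over a 12-month period".
- **Entry (Study Objectives).** The analysed patients are those with "diarrhea in adult patients admitted to four acute care hospitals in the Calgary region being tested for CDI". The mention of four hospitals conflicts with the single-hospital design, but that is a separate matter. Under Methods, isolation records are linked to CDI specimen results, so an untested patient with diarrhea contributes nothing.
- **Visibility of the arm (Study Objectives).** "NPT testing can deliver results within several hours, while typically off-site testing takes one to two days". No blinding is described.
- **Ordering and isolation (Background and Significance).** Where testing and treatment have separate budgets, "the hospital may decide to order more tests than is optimal". Isolation begins before any result: "patients with acute diarrhea of unknown cause are pre-emptively placed in private rooms with additional contact precautions". Its length is said to depend largely on the microbiology result.
- **Endpoints (Study Objectives).** "Our primary endpoint is to examine the differential effect of NPT on the duration of contact precautions". Secondary outcomes include "the incidence of CDI, severe CDI, and in-hospital mortality", with no denominator stated for incidence. A cost evaluation of both arms is also planned.
- **Protection against imbalance.** Methods relies on patient numbers and randomisation and sees no need for matching. The example regression under Data Analysis adjusts for age, gender, CDI status and severity, ward, and season or month. The one contingency, under Study Objectives, concerns differences in test performance.

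**The concern.** Randomising wards balances wards. It does not balance patients who are selected on those wards afterwards by staff who can tell which arm they are in. A negative result within hours offers a quick route out of isolation, which is a plausible reason to test patients at lower suspicion of CDI. If near-patient testing (NPT) wards did so, mean isolation per tested patient would fall without any patient spending less time isolated. If they instead tested patients who stay isolated longer, a real benefit would be masked.

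Sample size does not help, because selection bias does not shrink as numbers grow. The plan sets out no comparison of ordering rates or case mix by arm, and no isolation analysis on a denominator independent of testing. A reader of the results could not tell a shorter isolation from a changed denominator.

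**Working it through.** **1. The plan's own counts.** The documents give no mean or SD of isolation days, no ordering rate and no power calculation, so the only figures to reproduce are patient counts. As written, 39 per ward per month × 40 wards × 6 months = 9,360, against a stated 1,578. Reading 39 as a six-month figure gives 39 × 40 = 1,560, and for negatives 33 × 40 = 1,320 against a stated 1,300. I therefore use the six-month totals. Negatives are 1300/1578 = 82.4% and positives 278/1578 = 17.6%.

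**2. Unadjusted illustration, zero true effect.** Assumed: mean isolation of 3.0 days in patients who would be tested in either arm, and an extra fraction e tested on NPT wards, isolated x days each.

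NPT mean = (3.0 + e·x)/(1 + e)

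With e = 0.10 and x = 1: 3.1/1.1 = 2.82, a spurious saving of 0.18 day. Isolation days counted in the analysis rise by 3.1/3.0 − 1 = 3.3%.

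| Spurious saving (days) | x = 0.5 | x = 1 | x = 2 |
|---|---|---|---|
| e = 5% | 0.12 | 0.10 | 0.05 |
| e = 10% | 0.23 | 0.18 | 0.09 |
| e = 20% | 0.42 | 0.33 | 0.17 |

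**3. The same 10%, 1-day case adjusted for CDI status.** Assume all 157.8 extra patients are negative and positive patients average m days. The negative mean on control wards is (3.0 × 1578 − m × 278)/1300. The spurious saving among negatives is (157.8/1457.8) × (negative mean − 1), and among positives it is zero. A common arm effect weights each stratum by n0·n1/(n0 + n1): 687.2 for negatives and 139 for positives, so negatives carry 0.832 of the weight.

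| m (days) | Negative mean, control | Saving among negatives | Adjusted saving |
|---|---|---|---|
| 6 | 2.36 | 0.147 | 0.12 |
| 8 | 1.93 | 0.101 | 0.08 |
| 10 | 1.50 | 0.054 | 0.05 |

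If the extras are isolated 2 days each, the adjusted figure runs from a saving of 0.03 day (m = 6) to an apparent loss of 0.04 day (m = 10).

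**4. Reversed sign.** If the 10% extra are isolated 5 days each, the NPT mean is 3.5/1.1 = 3.18, an apparent loss of 0.18 day. In general the unadjusted bias is e/(1 + e) times the gap in mean isolation between extra and other patients. With 20% extra and a 3-day gap it is (0.2/1.2) × 3 = 0.5 day, enough to hide a true half-day reduction.

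**5. Scale against sampling error (unadjusted).** Take the 0.18-day bias, 1,578 control patients, an assumed SD of 3 to 7 days, an assumed design effect of 1 to 4 and a two-sided 5% test. The chance of a significant difference with no true effect is then about 7% to 41%.

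**6. Could the trial see a change in ordering?** In a simple Poisson comparison with 1,578 expected tests in the control arm, ignoring clustering, a 10% rise is detected with about 78% power and a 5% rise with about 28%.

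**The case against.** - **No evidence that ordering will differ.** The Background passage attributes over-ordering to tests that look free under separate budgets, and the intervention does not change that. Work-up of acute diarrhea is described as routine and entry requires diarrhea, which limits optional extra tests. This stands: an effect of speed on ordering is inference, and the pool may be small. It does not show the pool is empty.
- **The design and model already mitigate.** The crossover and ward dummies remove stable ward differences in ordering, but not a change when the ward switches arm. The CDI-status term cuts the 0.18-day case as shown. It cannot correct selection among negatives, who are 82% of tested patients, and CDI status among tested patients itself depends on who is tested.
- **The endpoint may exclude negatives.** Methods ties contact precautions to a window around a CDI diagnosis. Read literally, extra negatives would add no endpoint days. The hypothesis of avoiding unnecessary isolation in patients without CDI implies that negatives count. The two passages must be reconciled.
- **Not every outcome is a mean per tested patient.** A reader might infer that all are exposed in the same way. The documents do not support that: turn-around time is per specimen, incidence has no stated denominator, and a cost evaluation reported as arm totals would show extra testing as cost.
- **Total isolation need not rise.** The 3.3% applies to days counted in the analysis. If the extra patients would have been isolated anyway, the ward total is unchanged while the spurious saving remains.

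**Conclusion.** The concern holds as a risk that the plan can neither detect nor remove. Entry is decided after allocation by staff who can infer the arm, and a within-ward change in ordering would pass into the primary contrast.

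The size cannot be derived from the documents. In the illustrative case the spurious saving is 0.18 day unadjusted and about 0.05 to 0.12 day after adjustment for CDI status. This rests on an assumed 3.0-day mean, 10% extra tested patients, all negative and isolated 1 day, positive patients averaging 10 to 6 days, and test-negative patients counting in the primary endpoint. The direction depends on who the extra patients are.

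Two stronger readings are tempting. One is that NPT wards will test more; nothing in the documents shows this. The other is that the bias could reach the 0.42 day at the top of the unadjusted range; that figure ignores the adjustment in the plan's example model. The change is worth making, but the design is not invalid without it.

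**What to change.** Keep the tested-patient analysis as primary and add the following to the Data Analysis section.

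1. **Describe testing by arm and ward-period.** Report CDI tests per inpatient-day (or per admission), positivity, and baseline characteristics of tested patients. Model the testing rate on arm, ward and period. Report the rate ratio with its confidence interval; given the power above, a non-significant result would not exclude a modest change in ordering.
2. **Add a named sensitivity analysis of the primary endpoint.** Use isolation days with a recorded reason of diarrhea or CDI, per 1,000 inpatient-days, for all inpatients on the ward whether tested or not, by ward-period with terms for arm, ward and period. According to Methods, the clinical system already holds dates, care unit and reason. This is a more diluted estimand, so it supports the primary analysis and does not replace it.
3. **State whether test-negative patients count in the primary endpoint**, and reconcile the definition of contact precautions with the hypothesis.
4. **Interpret CDI incidence alongside the testing rate.** An inpatient-day denominator does not repair it, because the numerator still depends on who is tested.

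This is a cheap improvement: one more extract from the clinical system, probably a ward census extract for inpatient-days (the documents describe only encounter admission and discharge dates), a ward-level model, and a second, noisier estimate to report.

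### The only rule for which isolation orders count towards the primary endpoint is tied to a CDI diagnosis, which conflicts with a study population of everyone tested

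*Combined protocol and SAP*

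**What the plan says.** Study Objectives gives the primary endpoint as "the duration of contact precautions (i.e. patient isolation days", with no restriction by test result. Methods then has one sentence on which orders belong to it: contact precautions "due to CDI will be defined as an order by healthcare workers for contact precautions within the 7-day infection window of a CDI diagnosis". The next sentence gives the length as the date of completion, or of discharge, minus the date of the order, again without reference to the result.

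Methods does not say what counts as a CDI diagnosis. The seven-day window appears in one other place, the definition of severe CDI, where laboratory values count if collected "within a 7-day infection window around the date the laboratory tested positive for" *C. difficile*.

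Other parts of the plan bear on who should be covered:

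- Background and Significance says that "patients with acute diarrhea of unknown cause are pre-emptively placed in private rooms with additional contact precautions", that "the duration of patient isolation depends largely on the result of microbiological testing", and that among those screened "85% are negative on GDG screen and 89% are negative post PCR confirmation".
- Study Objectives says: "For patients without CDI, the antibiotics, and in many cases, the isolation, are unnecessary". It enrols adult inpatients with diarrhea who are tested for CDI, and expects 1,578 patients and a "total of 1300 negative pts in a 6-month period". It also plans to cost isolation for all patients in both arms.
- Methods takes isolation start and stop dates and the reason (CDI and diarrhea are the examples) from Sunrise Clinical Manager (SCM), and links them by health number to the specimens tested.
- Data Analysis names hours in isolation as an example outcome and lists CDI status among the covariates.
- Originality of the proposal puts enrolment at about 3,000.

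**The concern.** A window that needs a positive test date does not exist for a patient who tests negative. If a programmer applies the Methods sentence as it stands, the primary outcome exists only for positives. The trial would then miss the effect that Study Objectives puts forward for patients without CDI, namely unnecessary isolation avoided by an earlier negative result.

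The literal rule would also restrict the primary analysis by a test result obtained after randomisation. The two arms use different platforms. The stated evidence that they agree is a pilot of 20 samples, with a larger confirmation still to come.

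If the sentence is set aside instead, no rule is left for choosing orders. Isolation is pre-emptive, so an order may precede both the specimen and the result. The plan does not say how to treat an order already active at collection, a repeat specimen, or a tested patient with no order. Each choice affects the primary estimate, and each could be settled after the data are seen.

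**Working it through.** **Step 1. What each sentence settles.**

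| Element | What the plan gives | Works for a test-negative patient? |
|---|---|---|
| Endpoint statement (Study Objectives) | Duration of precautions, no limit by result | Yes |
| Which orders qualify (Methods) | Order within the window of a CDI diagnosis | Not if diagnosis means a positive test |
| Anchor of the window (Methods, severe CDI) | Date of a positive test | No |
| Length (Methods) | End date minus order date | Yes, for any order |
| Linkage (Methods) | By health number, to specimens tested | Yes, but with no time window |
| Isolation reason (Methods) | Collected | Yes, but no sentence uses it to select orders |
| Antibiotic therapy (Methods) | Started from the day of specimen collection to 48 hours after | Yes |

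Only the qualifying rule and its anchor fail. The antibiotic definition shows that the plan already has an anchor that works whatever the result.

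**Step 2. Reproduce the plan's counts** (Study Objectives; 40 wards).

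- Tested: 39 × 40 = 1,560, against 1,578 stated.
- Negative: 33 × 40 = 1,320, against 1,300 stated.

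Both agree closely if the ward means are per six months. Read per month, as labelled, 39 × 40 × 6 = 9,360, which does not fit. The six-month totals are used below.

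- Negative share: 1,300 / 1,578 = 82.4%. Background gives 89% after PCR confirmation.

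**Step 3. Reach of the literal rule over two periods.**

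- Tested: 2 × 1,578 = 3,156, somewhat above the approximate 3,000.
- Negative, from the counts: 2 × 1,300 = 2,600 (82.4%).
- Negative, at 89%: 0.89 × 3,156 = 2,809.
- Covered (positive), from the counts: 3,156 − 2,600 = 556 (17.6%).
- Covered (positive), at 89% negative: 3,156 − 2,809 = 347 (11.0%).
- Ward-periods: 40 × 2 = 80. Tested per ward-period: 3,156 / 80 = 39.5. Covered per ward-period: 347 / 80 = 4.3 to 556 / 80 = 7.0.

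These counts use two full six-month periods and take nothing off for wash-in and wash-out, whose lengths the plan does not give.

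**Step 4. What cannot be computed.** The documents do not give the share of tested patients with an isolation order, or the timing of orders relative to collection. The effect of the unstated choices on the estimate therefore cannot be sized from the plan.

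**The case against.** The best defence is that the endpoint is already general. The endpoint statement and the length formula are not limited to CDI, SCM isolation data are linked to all tested specimens, isolation is costed for all patients, and the model adjusts for CDI status, which would serve little purpose among positives alone. The sentence about precautions due to CDI could be describing a subset. In addition, Methods does not say that a diagnosis is a positive test; that anchor comes from a different variable.

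Much of this stands. A reader might infer that the sponsor decided to drop negatives, or that the endpoint has no definition at all for them. The documents support neither. The likely intent is all tested patients, and most of the definition serves them. Equating diagnosis with a positive test is also an inference, though it rests on the only anchor given.

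What does not stand is that general wording elsewhere cures the rule. The length formula says how to count days, not which orders to count. Linkage by health number without a time window does not choose orders either. If the sentence defines a subset, the rule for everyone else is missing; if diagnosis means something wider, that meaning is unstated.

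**Conclusion.** The order-qualifying rule is wrong as written: it conflicts with the all-tested population that the rest of the plan implies. Read literally, it gives a qualifying rule to 11-18% of tested patients and none to the other 82-89%, the group in whom avoidable isolation is expected.

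Those percentages hold only on the literal reading, with diagnosis taken as a positive test and with wash-in and wash-out ignored. They measure the reach of the faulty sentence. A reader might take them as the expected loss of data or as a bias in the result, but the documents do not support that, because the intended analysis probably includes negatives. On that likelier reading the fault remains that no rule selects their orders.

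**What to change.** Replace the sentence in Methods with a definition that covers every tested inpatient on a randomised ward, whatever the result. It should state:

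1. **Qualifying orders:** contact-precautions orders active at CDI specimen collection, or started within a fixed window around it. If seven days is kept, say whether that is the total or each side.
2. **Reasons:** the SCM isolation reasons that qualify, including diarrhea as well as CDI.
3. **Counting:** when counting starts for an order already active at collection (for example, from collection, since the testing arm cannot affect earlier days), running to order completion or discharge.
4. **Index specimen:** which specimen is used when a patient has repeats.
5. **No order:** tested patients with no order stay in the primary analysis (for example, scored as 0 days), so that the analysis does not select further on isolation status.
6. **CDI status:** results by CDI status as a secondary breakdown only.

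The anchors for severe CDI and antibiotic therapy can stay as they are. The change concerns measurement, not when patients are isolated. It costs protocol and SAP wording plus minor programming, because the SCM dates, reasons and health-number linkage are already planned. It should be settled before outcome data are examined.
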